Methocarbamol and Orphenadrine for Acute, Non-traumatic, Non-radicular Low Back Pain: A Randomized, Placebo Controlled, 3-armed Study

NCT#: NCT02665286 Protocol ID: 2015-5903 Version Date: 01/27/2016

[name] Professor and Vice-Chair for Clinical Investigations Department of Emergency Medicine Montefiore Medical Center Albert Einstein College of Medicine

Specific Aims

Low back pain (LBP) causes 2.4% of visits to US emergency departments (ED) resulting in 2.7 million visits annually. (1) In general, outcomes for these patients are unfavorable. One week after ED discharge, 70% of patients report persistent back-pain related functional impairment and 69% report analgesic use within the previous 24 hours.(2) Three months after the emergency visit, 48% of ED LBP patients report functional impairment, 42% report moderate or severe pain, and 46% report persistent analgesic use. (2)

It is not clear which medications should be prescribed for acute LBP. Non-steroidal anti-inflammatory drugs (NSAID) are more efficacious than placebo with regard to LBP relief, global improvement, and requirement of analgesic medication (3) but are insufficient treatment for as many as ½ of ED patients, who continue to suffer despite use of NSAIDs. Treatment of LBP with multiple concurrent medications is common in the ED--emergency physicians often prescribe skeletal muscle relaxants or opioids in combination with NSAIDs.(4) However, work recently completed has revealed that combining cyclobenzaprine, a skeletal muscle relaxant, or oxycodone/acetaminophen with an NSAID does not improve outcomes.(5) It remains uncertain if adding other skeletal muscle relaxants to NSAIDs improves LBP outcomes.

Two specific skeletal muscle relaxants, orphenadrine and methocarbamol, are each used in more than 250,000 U.S. ED visits for LBP annually, although scant evidence exists to determine the appropriateness of this approach.(6) Orphenadrine is centrally acting with prominent anti-cholinergic and anti-histaminic properties. Mechanism of action is not understood. Efficacy in low back pain may be related to non-specific analgesic properties. Mechanism of action of methocarbamol has also not been established. Its efficacy is thought to be related to CNS effects rather than direct effects on skeletal muscles.

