- Absence of non-musculoskeletal etiology of low back, such as urinary tract infection, ovarian cysts, or influenza like illness. The primary clinical diagnosis, at the conclusion of the ED visit, must be a diagnosis consistent with non-traumatic, non-radicular, musculoskeletal LBP.

-Patient is to be discharged home. Patients admitted to the hospital are more likely to be treated with parenteral medication and therefore are not appropriate for this study.

- Age 18-69 Enrollment will be limited to adults younger than 70 years because of the increased risk of adverse medication effects in the elderly.

-Non-radicular pain: pain cannot radiate below the gluteal folds in a radicular pattern. Patients with non-radicular pain extending below the gluteal folds will not be excluded

-Pain duration ≤ 2 weeks (336 hours). Patients with more than two weeks of pain are at increased risk of poor pain and functional outcomes.(2)

-Prior to the acute attack of LBP, back pain cannot have occurred once per month or more frequently. Patients with more frequent back pain are at increased risk of poor pain and functional outcomes.(2)

-Non-traumatic LBP: no substantial and direct trauma to the back within the previous month -Functionally impairing back pain: A baseline score of > 5 on the Roland-Morris Disability Questionnaire (Appendix)

Exclusion criteria:

-Not available for follow-up

-Pregnant or breast-feeding

-Chronic pain syndrome defined as use of any analgesic medication on a daily or near-daily basis -Allergic to or intolerant of investigational medications

-Contra-indications to non-steroidal anti-inflammatory drugs: 1) history of hypersensitivity to NSAIDs or aspirin or patients in whom NSAIDS or aspirin have induced allergic manifestations such as asthma, nasal polyps, rhinitis, or urticarial 2) active or history of peptic ulcer disease, chronic dyspepsia, or active or history of gastrointestinal bleed 3) Severe heart failure (NYHA 2 or worse) 4) hypertension (JNC7 stage 2 or worse) 5) Chronic kidney disease 3 or worse 6) Current use of anti-coagulants, bleeding with tooth brushing, easy bruisability 7) Hepatitis 8) Alcoholism

Naproxen plus orphenadrine or methocarbamol for LBP. An RCT. Version 012716

-Contra-indications to orphenadrine: 1) Glaucoma, Prostatic hypertrophy, Myasthenia gravis, Pyloric or duodenal obstruction

-Contra-indications to methocarbamol: 1) Myasthenia gravis, Chronic kidney disease 3 or worse

Study arms:

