3. Frequency of low back pain over the previous week using the five point Likert scale: Not at all, Rarely, Sometimes, Usually, Always

- 4. Number of days with LBP since ED discharge
- 5. Use of any analgesic or LBP medication within the previous 7 days.
- 6. Number of visits to any healthcare provider.
- 7. Satisfaction with medication and with the current state of the LBP

Adverse events

The following adverse medication effects will be assessed at the one week follow-up.

-CNS side effects including drowsiness and dizziness

-GI side effects including dyspepsia, nausea, and bleeding

-All other side effects

Randomization and blinding

The pharmacist will perform randomization in blocks of 6 based on a sequence generated at http://randomization.com. Every block of six will contain two orphenadrine assignments, two methocarbamol assignments, one placebo assignment dosed as 1 capsule twice daily (to mirror orphenadrine dosing), and one placebo assignment dosed as 1-2 capsules thrice daily (to mirror methocarbamol dosing). Therefore, though patients will not know whether they have been assigned to active medication or placebo, they may deduce to which medication they were not assigned. This does not threaten the internal validity of the study because patients will not know whether or not they received active medication.

Naproxen will not be masked. Orphenadrine, methocarbamol, and placebo will be masked by placing tablets into identical capsules, which will be packed with scant amounts of lactose and sealed. This masking will take place in a secure location inaccessible to ED personnel. Patients will be presented with two vials of medication. The vial containing the naproxen will be labeled in a typical manner. The second vial, containing orphenadrine, methocarbamol, or placebo will be labeled as investigational medication. Patients will be instructed to the investigational medication only as needed for moderate or severe LBP.

Details of protocol

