We based assumptions on a recently completed RCT of LBP treatment. The mean improvement in RMDQ among those who receive naproxen alone was 10.2. The standard deviation was 8.9. A widely accepted minimum clinically important improvement of 5 points on the RMDQ would require those randomized to active medication to demonstrate a mean improvement of 15.2 on the RMDQ. Using a standard alpha of 0.05 and a beta of 0.20, we determined the need for 50 subjects in each arm. To account for protocol violations and patients lost-to-follow-up (typical lost-to-follow-up rate is 5%) and to ensure sufficient power for the per protocol analysis (in our previous ED-based LBP studies, up to 1/3 of enrolled patients have not used the medication more than once), we intend to enroll 80 patients in each arm.

Data Safety Monitoring Committee. This committee will be headed by [name] and include XXX. The committee will meet every month with the PI to 1) monitor adverse events and develop strategies to minimize these; and, 2) monitor recruitment and enrollment. There will not be an interim analysis. Naproxen plus orphenadrine or methocarbamol for LBP. An RCT. Version 012716 6

Registration. The study will be registered at http://www.clinicaltrials.gov.

Consent. Study personnel will obtain informed consent once the patient's pain has been controlled and the patient is ready for discharge from the ED.

Risks/Benefits

Non-steroidals are used in 50% of more than 2.5 million annual US ED visits for LBP. Skeletal muscle relaxants are used in 43% of these visits. Regardless of results, this study will have a national impact. Study subjects will benefit by receiving a medication that is likely to improve their acute LBP. In addition to breach of confidentiality, which is unlikely, and inconvenience to the subject, which will undoubtedly occur, it is likely that subjects will experience adverse medication effects. For the most part, these are nuisance events. Skeletal muscle relaxants such as orphenadrine and methocarbamol are generally well tolerated but can cause substantial drowsiness and when combined with alcohol or other centrally acting substances may be lethal. Non-steroidals can cause life-threating gastro-intestinal bleeding, but this is unlikely in patients screened for gastro-intestinal illness who will take the medication for one week only.

Data Storage & Confidentiality

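### The one-week side-effect list names no anticholinergic symptom, so effects most specific to orphenadrine rest on an unspecified residual item and may be under-ascertained

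*Combined protocol and SAP*

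**What the plan says.** The Adverse events section introduces its list with "The following adverse medication effects will be assessed at the one week follow-up". Three lines follow: "CNS side effects including drowsiness and dizziness"; "GI side effects including dyspepsia, nausea, and bleeding"; and "All other side effects". The protocol contains no side-effect form and no wording for these questions. The appendices reproduce only the Roland-Morris (RMDQ) and Cassandra items, although several efficacy questions are given verbatim under Outcome measures.

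On the drugs, Specific Aims states: "Orphenadrine is centrally acting with prominent anti-cholinergic and anti-histaminic properties". It says nothing comparable about methocarbamol. Exclusion criteria gives the orphenadrine contraindications as "Glaucoma, Prostatic hypertrophy, Myasthenia gravis, Pyloric or duodenal obstruction". Of these four, only myasthenia gravis is also listed for methocarbamol. Risks/Benefits describes the relaxants as "generally well tolerated but can cause substantial drowsiness", and for naproxen it mentions gastrointestinal bleeding.

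The Analysis paragraph reports secondary outcomes as rates with 95% confidence intervals. It states no significance test for side effects.

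**The concern.** The five named symptoms match the risks that Risks/Benefits describes: sedation from both relaxants, and gastrointestinal effects of naproxen, which every arm receives. They do not match the property that the protocol singles out for one active arm. Dry mouth, blurred vision, difficulty urinating and palpitations have no obvious place except the residual line. Constipation would fall under the gastrointestinal line but is not named there. (The documents list no anticholinergic symptoms; these are the usual ones, and the investigators should confirm the list.)

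A symptom asked about by name is often ascertained more completely than one a patient must think to mention. If that holds here, the effects that best distinguish orphenadrine from placebo sit in the least sensitive part of the list. Any benefit on the RMDQ has to be weighed against tolerability, and an attenuated absolute difference would tilt that comparison in orphenadrine's favour. Symptoms not asked about at the one-week call cannot be reliably recovered afterwards.

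**Working it through.** **Number available.** The plan gives no side-effect rate, capture rate or side-effect power, so its only reproducible figure is the sample size.

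- Inputs from Sample size calculation: difference 5, standard deviation 8.9, alpha 0.05 (taken as two-sided), power 0.80.
- n per arm = 2 × (1.960 + 0.842)² × 8.9² / 5² = 2 × 7.85 × 79.21 / 25 ≈ 49.7, so 50, as stated. The exact t-test solution is 50.7.
- Enrolment is 80 per arm with 5% lost: 80 × 0.95 = 76 followed per arm. If one third do not use the drug adequately, 76 × 2/3 ≈ 50.7 remain, which is consistent with the plan.

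None of this changes under the present point. It only supplies the 76 used below.

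**Effect of incomplete capture.** Let p₁ and p₀ be the true risks of an anticholinergic symptom on orphenadrine and placebo, and s the fraction that the residual item records. The list is the same for all arms and the drug is masked, so take s as equal in both arms.

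- Observed risk ratio = s·p₁ / s·p₀ = p₁/p₀, unchanged.
- Observed risk difference = s·(p₁ − p₀), reduced by the factor s.
- Events missed per arm = 76·(1 − s)·p, which is larger in whichever arm truly has more events.

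**Illustration.** Every rate and every s below is an assumption; none comes from the documents. Cells show the observed risk difference in percentage points.

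| True risks | s = 1 | s = 0.75 | s = 0.5 | s = 0.25 |
|---|---|---|---|---|
| 20% vs 5% | 15 | 11.3 | 7.5 | 3.8 |
| 30% vs 10% | 20 | 15 | 10 | 5 |
| 15% vs 5% | 10 | 7.5 | 5 | 2.5 |

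For 20% vs 5% at s = 0.5, the events missed are 76 × 0.5 × 0.20 = 7.6 on orphenadrine and 76 × 0.5 × 0.05 = 1.9 on placebo.

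**Precision.** A 95% interval is the plan's style of reporting for secondary outcomes. Half-width = 1.96 × √[(p₁(1 − p₁) + p₀(1 − p₀))/76].

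- Full capture, 20% vs 5%: 1.96 × √[(0.16 + 0.0475)/76] = 10.2 points, so the interval is 4.8 to 25.2.
- Half capture, 10% vs 2.5%: 1.96 × √[(0.09 + 0.0244)/76] = 7.6 points, so the interval is about −0.1 to 15.1.

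Under these assumptions, a difference clearly above zero would become one that is not.

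**As a test, for scale only.** Exact two-sided Fisher power at 76 per arm:

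| True risks | s = 1 | s = 0.5 |
|---|---|---|
| 25% vs 5% | 93% | 56% |
| 20% vs 5% | 77% | 34% |
| 30% vs 10% | 84% | 45% |
| 15% vs 5% | 45% | 16% |

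The level depends heavily on the rates chosen: 10% vs 3% gives only 29% at full capture. The direction does not.

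**The case against.** Several objections have force.

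- **The list is not closed.** Both named lines are introduced as examples and a residual line follows. A reader might infer that only CNS and gastrointestinal symptoms are collected. The text does not support that: anticholinergic effects are within planned collection.
- **No elicitation method is stated.** A reader might infer that the named symptoms are read out and the rest must be volunteered. The protocol says neither. Lower sensitivity of the residual item is therefore a condition of this point, not a documented fact.
- **The arms are treated alike.** The list is common and the study drug is in identical capsules. A reader might infer that orphenadrine's events will be under-counted in that arm alone, or that the whole tolerability comparison is biased. Neither follows. Reduced capture would apply to every arm, the risk ratio would hold under equal capture, and drowsiness, the effect that Risks/Benefits stresses, is named.
- **The power figures are illustrative.** They rest on assumed rates and on a test the plan does not state for side effects. The drug is also taken as needed, so not all 76 would be fully exposed.
- **There are other routes.** Healthcare visits are recorded at both follow-ups, and the safety committee is not said to rely on the one-week list alone. The exclusions also remove some patients at risk.

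What remains is narrower. Identical questions and masking do not restore a shrunken absolute difference. Healthcare visits are an unlikely route for symptoms such as dry mouth. And leaving the wording open lets interviewers differ.

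**Conclusion.** The point holds as a risk of under-ascertainment. The protocol identifies a prominent pharmacological property of one active drug, excludes patients with conditions specific to that drug's contraindications, and then names no corresponding symptom in its safety assessment. If the residual item captures a fraction s of these effects in every arm, the absolute orphenadrine-placebo difference is multiplied by s and orphenadrine looks better tolerated; the ratio does not move. This rests on three assumptions: the residual item is less sensitive than the named ones, capture is equal across arms, and orphenadrine truly causes more of these effects. The documents fix no value for s or for the true rates, so the size is unknown. The primary outcome, both hypotheses and the sample size are untouched. It is a cheap improvement to a secondary safety measure and is worth making.

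**What to change.** Write out the one-week side-effect questions and add a short named group: dry mouth, blurred vision, difficulty urinating and palpitations. Add constipation to the gastrointestinal items. Ask every patient in every arm with the same yes/no wording, after the RMDQ and pain items so that the questions cannot colour the efficacy answers. Report the group by arm as rates with 95% confidence intervals, beside the CNS and gastrointestinal groups, and keep the residual item.

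The cost is about five yes/no questions, roughly a minute on a call already planned. Prompting will somewhat raise the count of minor events in all arms, placebo included, so the group should be read as a comparison between arms. The change concerns measurement only.

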Given the poor pain and functional outcomes that persist beyond an ED visit for acute LBP, we propose a clinical trial to determine whether combining either orphenadrine or methocarbamol with an NSAID is more effective than NSAID monotherapy for the treatment of acute, non-traumatic, non-radicular low back pain. Specifically, we will evaluate the following two hypotheses:

- 1) A daily regimen of naproxen + orphenadrine will provide greater relief of LBP than naproxen + placebo one week after an ED visit, as measured by the Roland Morris Disability Questionnaire
- A daily regimen of naproxen + methocarbamol will provide greater relief of LBP than naproxen + placebo one week after an ED visit, as measured by the Roland Morris Disability Questionnaire

Overview.

This will be a single center, double-blind, comparative effectiveness study, in which we enroll patients during an ED visit for musculoskeletal LBP and follow them by telephone seven days and three months later. Every patient will receive standard-of-care therapy, consisting of naproxen and a low back pain education session. Patients will be randomized to orphenadrine, methocarbamol, or placebo.

Subject selection:

Our goal is to include in this study a broad representation of patients with musculoskeletal back pain who are likely to respond to the investigational medications and who would not be considered candidates for spinal surgery or targeted epidural intervention. We hope for a widely generalizable study and therefore will not require diagnoses to be contingent on advanced imaging studies. Though we could ensure a more homogeneous study population by requiring imaging, we do not believe this is clinically useful and it will not facilitate dissemination and utilization of the study results. The presence or absence of palpable spasm of the paraspinal muscles will be recorded but not used as an entry criterion because the clinical significance and reliability of this finding is uncertain.(7)

Inclusion criteria:

-Present to ED primary for management of LBP, defined as pain originating between the lower border of the scapulae and the upper gluteal folds. Flank pain, that is pain originating from tissues lateral to the paraspinal muscles, will not be included.

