Prior to discharge from the ED and after the patient's pain has been controlled, the attending emergency physician will refer appropriate patients to study personnel for screening. Eligible patients would have already received different and various medications in the ED for their pain (potentially including naproxen) prior to being approached for study participation. This decision is up to the attending physician and is not related to participation in the study. Patients will be screened and consented. Research associates will ascertain baseline socio-demographic information, low back pain history, and baseline variables discussed above. A urine pregnancy test will be performed. Research personnel will provide each patient with a 15-minute educational intervention. This will be based on NIAMS's Handout on Health: Back Pain information webpage (available at http://www.niams.nih.gov/Health Info/Back Pain/default.asp) Research personnel will review each section of the information sheet with the patient and elicit questions. Patients will be discharged with two medical vials, one containing naproxen and one containing placebo, orphenadrine, or methocarbamol. Patients will be cautioned not to take off protocol LBP medications without first consulting with a healthcare provider. Patients will be cautioned not to drink alcohol or use other centrally-acting substances while using study medications. Patients will be cautioned not to drive after taking the study medications. Follow-up phone calls will be conducted one week and three months after ED discharge. Follow-up will be attempted daily until successful. For patients difficult to contact, express courier or home visit will be used to obtain follow-up information. Analysis. An intention-to-treat analysis will be performed. The primary outcome will be a comparison of the change in RMDQ between baseline and one week. Results will be reported as means with 95%CI. A t-test for independent samples will be used to determine statistically significant differences

between placebo and each of the active medications. Secondary outcomes will be reported as rates with 95%CI. A per protocol efficacy analysis will be conducted among those patients who use the investigational medication at least once.

Sample size calculation

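### One fixed block size of six with an unmasked dosing schedule could let enrolling staff foresee the next schedule, though not active versus placebo, for at most a quarter of assignments on average

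*Combined protocol and SAP*

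**What the plan says.** The section on randomization and blinding fixes a single block size: "The pharmacist will perform randomization in blocks of 6". It also fixes the contents: "Every block of six will contain two orphenadrine assignments, two methocarbamol assignments", plus one placebo given on the twice-daily orphenadrine schedule and one given on the thrice-daily methocarbamol schedule. All capsules look alike.

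The section accepts that the schedule carries information, since of patients it says "they may deduce to which medication they were not assigned". It then sets the matter aside: "This does not threaten the internal validity of the study because patients will not know whether or not they received active medication".

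The Overview describes one site ("This will be a single center, double-blind, comparative effectiveness study"), and no stratification is mentioned, so there is one sequence. Under the details of the protocol, "the attending emergency physician will refer appropriate patients to study personnel for screening", and those personnel obtain consent before the patient leaves with two vials. The protocol does not say who explains the dosing, whether the schedule is printed on the investigational vial, or whether the block size is withheld from recruiters. Its stated safeguards are that a pharmacist runs the randomization and that capsules are filled where ED personnel have no access.

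**The concern.** The protocol's defence answers a question about blinding: can a patient, once assigned, tell whether the capsules are active? Allocation concealment is a different question: can the person deciding whom to enrol foresee the next assignment? The protocol does not discuss it.

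Identical capsules hide the contents but not the regimen. The patient has to be told to take one capsule twice a day, or one or two capsules three times a day. The quantity may also show it: seven days' supply is 2 × 7 = 14 capsules on one schedule and up to 2 × 3 × 7 = 42 on the other. With exactly three of each schedule in every block of six, someone who counts enrolments can work out which schedules remain.

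At stake is selective enrolment. A recruiter who knows that the next slot is thrice daily knows that orphenadrine is ruled out, and the reverse holds for methocarbamol. Each drug sits wholly on one schedule while the pooled placebo arm is half on each. A difference in who is enrolled under the two schedules would therefore enter both primary comparisons, and the planned unadjusted t-tests would not remove it.

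**Working it through.** **Inputs.** From the randomization section: blocks of six, with 2 orphenadrine + 1 placebo = 3 twice-daily slots and 2 methocarbamol + 1 placebo = 3 thrice-daily slots. From the sample size section: SD 8.9, target difference 5 points, alpha 0.05, beta 0.20, 80 patients per arm.

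**The plan's own figures.** The protocol gives no figure for predictability. Its sample size reproduces (two-sided alpha assumed, normal approximation): 2 × (1.96 + 0.84)² × 8.9² / 5² = 49.7, so 50 per arm. The block scheme fits the enrolment target: 240 / 6 = 40 blocks, giving 80 orphenadrine, 80 methocarbamol and 40 + 40 placebo.

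**Certain prediction.** The next schedule is certain when all slots left in the block share it. Over the 20 equally likely orderings of three and three, the run of identical schedules at the end has length 1 in 12 orderings, 2 in 6 and 3 in 2.

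- Mean per block: (12 × 1 + 6 × 2 + 2 × 3) / 20 = 30 / 20 = 1.5.
- Share: 1.5 / 6 = 25%, or 60 of 240 assignments.
- By position: slots 1 to 3 never, slot 4 in 10% of blocks, slot 5 in 40%, slot 6 always.

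**Best guess.** Always naming the schedule with more slots left, and tossing a coin at ties, is right 4.1 times in 6 = 68.3%, against 50% by chance.

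**What is revealed.** Over all 180 arm orderings of a block, 2/3 of the predictable slots are active and 1/3 placebo. That is the same split as overall, so active versus placebo is not disclosed.

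**Effect on the contrasts.** Let d be the difference in mean expected change, twice-daily minus thrice-daily, between patients enrolled under the two schedules. Measured from the thrice-daily mean, the orphenadrine arm is at d, the methocarbamol arm at 0 and the pooled placebo arm at d/2. The orphenadrine contrast shifts by d − d/2 = +d/2 and the methocarbamol contrast by 0 − d/2 = −d/2.

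**Steering needed.** Let D be the difference in expected change between patients steered to one schedule and patients steered to the other. A contrast shift of 0.5 point needs d = 1.

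| Steering | d | D needed for d = 1 |
|---|---|---|
| Only on certain slots | 0.25 × D | 1 / 0.25 = 4 points |
| On every best guess | (0.683 − 0.317) × D ≈ 0.367 × D | 1 / 0.367 ≈ 2.7 points |

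**Scale.** The standard error of a contrast at 80 per arm is 8.9 × √(2/80) = 1.41. A 0.5-point shift is 0.5 / 1.41 ≈ 0.36 standard errors and one tenth of the 5-point target. It would raise the two-sided type I error of a contrast from 5% to about 6.5%.

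**Alternative lists.**

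| List | Certain in advance | Best guess right |
|---|---|---|
| Fixed blocks of 6 | 25% | 68.3% |
| Fixed blocks of 12 (6 + 6 schedules) | (12/7) / 12 = 14.3% | 64.3% |
| Blocks of 6 and 12 in random order | about 6% | about 66% |

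The last row is simulated for 240 patients. The two sizes are equally likely, and staff know the possible sizes but not their order.

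**The case against.** A reader might infer that staff will know a quarter of the assignments. The documents do not support that. The 25% requires recruiters to see or learn every earlier schedule, know the block size, follow block ends without a gap and, if there are several of them, share what they know. The protocol puts the block size in its text but states none of the other conditions. This part of the objection stands: 25% is a ceiling.

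A reader might also infer that the double blind is broken. It is not, because a known schedule never separates active from placebo. The usual motive for steering, to obtain or avoid placebo, is therefore absent. What remains is a preference between two drugs for which the Specific Aims say there is little evidence. A wish to keep a patient away from a contraindicated drug is largely removed as a motive, because the listed contraindications to either drug exclude a patient from the whole trial. Opportunity is also limited: patients are referred by the attending physician and consented when ready to go home, so deferral would mean holding someone until another enrolment used up the known slot. Leaving a patient out is easier.

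These arguments stand and keep the likely bias small. They do not close the gap, because nothing in the plan hides past schedules from recruiters. Fixed small blocks with a pharmacist-held list are a common choice, but here half of each block can be told from the other half by schedule.

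**Conclusion.** The concern holds in a limited form. One fixed block size, a visible schedule and a single sequence leave allocation concealment weaker than it need be, and the protocol's assurance does not cover this. The size is at most 25% of assignments with a schedule certain in advance on average, and 68% best-guess accuracy. Both figures depend on staff seeing earlier schedules, knowing the block size and tracking block ends.

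It would be wrong to read this as an expected bias of 0.5 point. That figure assumes d = 1, which takes a D of about 4 points if only certain slots are steered, or about 2.7 if every guess is acted on. Both are large beside the 5 points the protocol treats as the minimum important improvement. The sample size is not affected. This is an optional improvement, worth making because it costs little.

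**What to change.** Before enrolment, generate the list with blocks of 6 and 12 in random order, keeping the same proportions within each block. Let only the pharmacist hold it, and keep the block sizes out of any text available to enrolling staff. It would also help to state who gives the dosing instructions and whether that person recruits.

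Certain prediction falls from 25% to about 6% even if the possible sizes become known. Best-guess accuracy falls only to about 66%, so the gain is mainly in removing certainty. The cost is a new list, a small edit to the protocol and a possible imbalance of a few patients if enrolment stops mid-block.
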